Comprehensive Cancer Center of Wake Forest University
A Pilot Study: Open-Label Clinical Trial of CPI-613 in Patients with Advanced Bile Duct
Cancers
CCCWFU # 59212

Principal Investigator: [name] [name]
Section on Hematology and Oncology
Wake Forest School of Medicine
[name]
[name]

Co-Investigators: A. [name]
Department of Radiation Oncology
Wake Forest School of Medicine

Biostatistician: [name], PhD
Division of Public Health Sciences
Comprehensive Cancer Center of Wake Forest University

Research Nurse: [name] [name]
Comprehensive Cancer Center of Wake Forest University

Data Manager: [name]
Comprehensive Cancer Center of Wake Forest University

Regulatory / Budget: [name]
Comprehensive Cancer Center of Wake Forest University

Investigational Drug: CPI-613

IND Number: 117,500

Drug Sponsor: Cornerstone Pharmaceuticals, Inc.

Version Date: 07.16.18
02.28.18
02.22.17
02.16.16
10.22.15
06.16.15

Comprehensive Cancer Center of Wake Forest University
A Pilot Study: Open-Label Clinical Trial of CPI-613 in Patients with Advanced Bile Duct
Cancers
CCCWFU # 59212

[figure not shown]
04.23.15
01.21.15
11.14.14
09.08.14
07.24.14
06.19.14
05.20.14
02.28.14
08.16.13
07.16.13
04.23.13
04.05.13
02.08.13
02.04.13
12.19.12

Proprietary and Confidential

SCHEMA

Patients with histologically
and cytologically proven
bile duct cancer

Comprehensive Cancer Center of Wake Forest University
A Pilot Study: Open-Label Clinical Trial of CPI-613 in Patients with Advanced Bile Duct
Cancers
CCCWFU # 59212

Primary Objective

To evaluate the safety and anti-cancer activities (assessed based on Response Rate) of CPI-613 in patients with advanced unresectable bile duct cancer who have failed available therapies.

Secondary Outcome measures

- Progression-free survival
- Overall Survival

Design

Open-label single arm

* Maximum number of cycles allowed is 12, unless the investigator considers additional treatment can provide clinical benefit

** Two additional cycles will not be given if the patient no longer meets eligibility criteria, has worsening of biliary function, or has symptomatic progression.

Comprehensive Cancer Center of Wake Forest University
A Pilot Study: Open-Label Clinical Trial of CPI-613 in Patients with Advanced Bile Duct
Cancers
CCCWFU # 59212

Table of Contents

1. BACKGROUND AND STUDY OBJECTIVES.....	6
2. STUDY DESIGN.....	7
2.1 Study Objective.....	7
2.2 Outcome Measures.....	7

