2.2 Outcome Measures

The primary outcome measures are safety and anti-cancer activities (assessed based on Response Rate [RR]).

The secondary outcome measures are:

- Progression-Free-Survival (PFS).
- Overall Survival (OS).

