According to the Response Evaluation Criteria in Solid Tumors (RECIST), the efficacy of treatment for solid tumors is determined by the tumor size. RECIST criteria are the golden standard to evaluate the tumor. In this study RECIST criteria will be used to evaluate response. However, there is a *pseudoprogression* phenomenon described with the use of CPI-613 in Phase I solid tumor studies (Lee et al. 2012).

It is felt that if CPI-613-induces necrosis of the tumor lesion there may be some radiographic evidence for increasing size. CPI-613 induces tumor necrosis due to its mechanism of action – selectively targeting the altered form of mitochondrial energy metabolism in tumor cells, causing changes in mitochondrial enzyme activities and redox status, which leads to apoptosis, necrosis, and autophagy of tumor cells (2,3,7,17,18).

For the purposes of this study, pseudoprogression will be defined and considered in patients who meet RECIST criteria of progression. It will be the treating physician's discretion to continue treatment in this situation if the patient is deemed to be getting clinical palliative benefit. In these patients, the study drug can be given for another two cycles prior to making definitive determination of progression or response.

Assessment of tumor response will be the responsibility of the principal investigator and should be based on radiologic findings (i.e., contrast CT of the chest, abdomen, and pelvis, and MRI of the abdomen), CA-19-9 and performance status.

OS will be monitored bimonthly via telephone contact after treatment termination. (**Note:** During the bimonthly post-study telephone contact, information related to cancer treatment received after the study will also be collected). OS and PFS will be calculated from the first day of treatment. The duration of OS will be measured until the date of death or censored at follow-up. The duration of response (evaluated by PFS) will be measured from the date a first objective response is documented until the first sign of progression assessed by MRI and CT.

****NOTE:** Tumor necrosis alone should not be criteria for determining

Comprehensive Cancer Center of Wake Forest University
A Pilot Study: Open-Label Clinical Trial of CPI-613 in Patients with Advanced Bile Duct
Cancers
CCCWFU # 59212

progression.

Safety and RR of CPI-613 are the primary endpoints, whereas PFS and OS are secondary endpoints.

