6.1 Dose Levels, Dose Escalation, Sample Size and Justification of the Dose

6.1.1 Dose Levels, Dose Escalation and Sample Size

The dose levels to be used in assessing the safety and anti-cancer activities of CPI-613 in 10 patients with advanced bile duct cancers will be determined from a dose-escalation scheme using cohorts of patients with advanced bile duct cancers, as described below. The dose-escalation scheme is based on the number of patients exhibiting dose-limiting toxicity (DLT), and DLT is defined as toxicity of Grade 3 or higher attributed as probably or definitely related to CPI-613. The DLT determining period for all cohorts in the dose-escalation scheme is through the first cycle.

Comprehensive Cancer Center of Wake Forest University
A Pilot Study: Open-Label Clinical Trial of CPI-613 in Patients with Advanced Bile Duct
Cancers
CCCWFU # 59212

Cohort 1: The first 3 patients will not be treated with the 5 daily doses of CPI-613 during the pre-Cycle 1 week, and will only be treated with 3-weeks-on-1-week-off treatment cycles (see Table 6-1). The dose of CPI-613 will be 2,300 mg/m² (which is approximately three-quarters of the target dose). If none of these 3 patients develop a dose-limiting toxicity (DLT) through Cycle 1, the dose for the 3-weeks-on-1-week-off treatment cycles will be 3,000 mg/m² in all subsequent patients in this trial. However, if a DLT is observed in a patient (whether it is the 1st, 2nd or 3rd of the 3 intended patients), the number of patients in this cohort will be expanded to a maximum of 6 patients. If no DLT is observed in another patient out of a maximum of 6 patients, the dose for the 3-weeks-on-1-week-off treatment cycles will be 3,000 mg/m² in all subsequent patients in this trial. However, once DLT is observed in 2 patients, no additional patients will be treated at 2,300 mg/m² for the 3-weeks-on-1-week-off treatment cycles from that point on, even though the total number of patients in this cohort is as few as 2. The dose level of 2,300 mg/m², which induces a DLT in 2 or more patients, is considered to be above the maximum tolerated dose (MTD) for the 3-weeks-on-1-week-off treatment cycles. In this case, all subsequent patients in this trial will be treated at 1,700 mg/m² for the 3-weeks-on-1-week-off treatment cycles.

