even though the total number of patients at this cohort is as few as 2. The dose level of 3,000 mg/m²/day during the pre-Cycle 1 week, which induces a DLT in 2 or more patients, is considered to be above the MTD for the pre-Cycle 1 week. In this case, the dose of CPI-613 for the pre-Cycle 1 week in subsequent patients in this trial will be 2,300 mg/m²/day

Cohort 5: This cohort is performed once the dose of CPI-613 for the 3-weeks-on-1-week-off treatment cycles has been determined from Cohort 1, and once the dose of CPI-613 for the pre-Cycle 1 week has been determined from Cohort 2-4. There are 10 patients in this cohort. These patients will be treated with CPI-613 for 5 days during the pre-Cycle 1 week at doses as determined from Cohorts 2-4, and the dose of CPI-613 for the 3-weeks-on-1-week-off treatment cycles will be as determined from Cohort 1.

As can be seen by the above scheme there are several possible scenarios that could occur in order to determine the dose for the 10 patients to be evaluated in the pilot trial. Once the above procedure is completed we will then enroll 10 patients at the determined dose.

Accrual Rate

We anticipate accruing one patient per month for this protocol. Since the dose escalation procedure described above may involve a variable number of patients (at least 6 but possibly more) we cannot be certain the entire length of accrual for this protocol. However, we do anticipate that the total number of patients in this protocol will be between 16-40 (with 16-22 being the most likely range). Thus, we anticipate that we will reach the target sample size of 10 patients treated at MTD within two years. A minimum of 16 patients to a maximum of 40 patients will be accrued to the study, with the first 6-30 being evaluated for toxicity in a dose-escalated manner for determining the MTD, and the remaining 10 used in the analytic sample.

Proposed Analyses

The analyses for this protocol will be primarily descriptive. With a sample size of 10 treated at MTD, we do not expect to see statistically significant effects for the outcomes of interest, however this data will provide useful preliminary data on the overall safety and efficacy of CPI-613 and provide useful data to predict the variability and likely effect sizes for these outcomes.

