For the time-to-event outcomes we will estimate survival curves for OS and PFS using Kaplan-Meier techniques. In addition, we will estimate the 6 month and 1-year OS and PFS rates for these participants. For response rate we will present the proportion of patients who are CR, PR, SD or PD. In addition, we will estimate the proportion of responders as the percent of patients who are CR or PR. For this rate we will also include a 95% confidence interval.

We will also examine toxicities for these 10 patients by looking at each toxicity identified earlier in the protocol by grade.

Sample Size Considerations

Since this is a pilot study we do not anticipate having statistical power to detect specific effects, however with this sample size we will be able to estimate the response rate using a 2-sided 95% confidence interval with an interval that will extend no more than 0.31 from the observed

Comprehensive Cancer Center of Wake Forest University
A Pilot Study: Open-Label Clinical Trial of CPI-613 in Patients with Advanced Bile Duct
Cancers
CCCWFU # 59212

response rate.

Comprehensive Cancer Center of Wake Forest University
A Pilot Study: Open-Label Clinical Trial of CPI-613 in Patients with Advanced Bile Duct
Cancers
CCCWFU # 59212

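### Safety is a primary outcome, but the only planned end-of-study toxicity analysis covers the 10 Cohort 5 patients and leaves out every dose-escalation patient and DLT

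*Combined protocol and SAP*

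**What the plan says.** Safety is primary in three places. The Schema's primary objective is "To evaluate the safety and anti-cancer activities (assessed based on Response Rate) of CPI-613"; Section 2.2 states "The primary outcome measures are safety and anti-cancer activities"; Section 5.1.3 states "Safety and RR of CPI-613 are the primary endpoints".

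The Proposed Analyses part of Section 9.0 has a single sentence on toxicity: "We will also examine toxicities for these 10 patients by looking at each toxicity identified earlier in the protocol by grade". The Accrual Rate paragraph just before it divides the patients in two: "the first 6-30 being evaluated for toxicity in a dose-escalated manner for determining the MTD", and "the remaining 10 used in the analytic sample". Section 6.1.1 frames the safety assessment the same way, as "assessing the safety and anti-cancer activities of CPI-613 in 10 patients with advanced bile duct cancers". The expectation that "this data will provide useful preliminary data on the overall safety and efficacy of CPI-613" follows directly from a reference to the 10 patients treated at the MTD.

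Data collection is not restricted in this way. Section 5.1.2 assesses safety from first dose to one month after last dose without naming cohorts, Section 8.1 has all Grade 3 to 5 events recorded, and the Appendix C log has a DLT field. The opening of Section 9.0 says in general terms that the trial will add to the safety profile, but names no analysis set or output. That same paragraph gives response rate alone as the primary goal, which differs from the three statements above.

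**The concern.** DLT counts in the escalation cohorts decide the regimen given to Cohort 5. If the analysis section is followed as written, the final result for a primary outcome contains none of those events and none of the patients in whom they were looked for. A reader would see toxicity at the selected regimen but not the evidence that selected it.

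The direction of the effect depends on the path. If a cohort closes because two patients had DLTs, that toxicity is missing and the drug looks better tolerated than the trial found. If the lower-dose cohorts clear, the omitted patients may have had less toxicity than Cohort 5. Pooling alone would not settle this; results are needed by cohort.

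**Working it through.** **1. The plan's own figures.** Inputs from the Accrual Rate paragraph of Section 9.0: 6 to 30 escalation patients, 10 in the analytic sample, 16 to 40 in total, 16 to 22 most likely. Check: 6 + 10 = 16 and 30 + 10 = 40. The maximum of 30 is five escalation cohorts (1, 2, Sub-Cohort 2, 3, 4) of 6 patients each.

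**2. Share of treated patients omitted** = escalation / (escalation + 10).

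| Case | Escalation | Total | Omitted |
|---|---|---|---|
| Stated minimum | 6 | 16 | 37.5% |
| Top of most likely range | 12 | 22 | 54.5% |
| Stated maximum | 30 | 40 | 75% |

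The stop-at-two-DLTs rule lets a cohort close with 2 patients, so totals below the stated minimum are also possible: 4/14 = 28.6% and 5/15 = 33.3%. The omitted patients then include at least 4 DLTs (total 14) or at least 2 (total 15).

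**3. Escalation patients if no DLT occurs.** This depends on how Cohort 3 is entered, where the text conflicts. The Cohort 2 paragraph sends the trial to Cohort 3 after 0 DLTs in 3 patients, giving 3 + 3 + 3 + 3 = 12. The Cohort 3 paragraph, read literally, opens that cohort only if a DLT was seen in Cohort 2 (or through Sub-Cohort 2). A clean Cohort 2 is then assumed to lead straight to Cohort 5, giving 3 + 3 = 6. The omitted share is 12/22 or 6/16.

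**4. Chance that at least one escalation DLT is omitted.** The documents give no DLT rate, so a flat rate *p* per patient is assumed, with patients independent. The probability is 1 − (1 − *p*)^12 under the Cohort 2 text and 1 − (1 − *p*)^6 under the literal Cohort 3 text.

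| *p* | Cohort 2 text | Literal Cohort 3 text |
|---|---|---|
| 5% | 46.0% | 26.5% |
| 10% | 71.8% | 46.9% |
| 20% | 93.1% | 73.8% |
| 30% | 98.6% | 88.2% |

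With an assumed rising rate (5, 5, 10, 20 and 30% in Cohorts 1, 2, Sub-Cohort 2, 3 and 4), the values are 1 − 0.95^6 × 0.80^3 × 0.70^3 = 87.1% and 1 − 0.95^6 = 26.5%.

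**5. Exact enumeration of the escalation paths.** Patients enter one at a time; a cohort stops at 2 DLTs and clears at 0 of 3 or 1 of 6. At flat rates of 5/10/20/30%:

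| Quantity | Cohort 2 text | Literal Cohort 3 text |
|---|---|---|
| Mean share omitted | 57.1 / 57.5 / 54.5 / 50.0% | 42.0 / 44.7 / 46.1 / 44.9% |
| P(total 14 or 15) | 0.2 / 0.8 / 2.7 / 6.2% | 0.4 / 1.5 / 4.8 / 9.3% |

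The probability of reaching 40 patients is at most 0.05% at these rates under either reading.

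**The case against.** The toxicity sentence does not say that only these 10 patients will be examined. Read with the Accrual Rate paragraph, the plan has two toxicity evaluations: DLT-based for escalation, then by grade for Cohort 5. The escalation rules cannot be applied without counting patients with DLTs in each cohort, all Grade 3 to 5 events are recorded, and nothing suggests that results would be suppressed. Concentrating on the selected regimen is also a reasonable choice for a descriptive pilot, particularly since Cohort 1 receives no pre-Cycle 1 week and so has a different regimen.

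Part of this stands. Data capture is not at fault, a sponsor may report the escalation data anyway, and a pooled column mixes doses. The 40-patient maximum and the totals of 14 and 15 are unlikely, so 6/16 and 12/22 are the more useful shares. The probabilities in step 4 show that DLTs may well be omitted, not how far the safety picture would shift.

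It does not remove the concern. Counting DLTs for a go/no-go decision is not an end-of-study output, and Appendix C is a capture form. The analysis section names its toxicity population explicitly and sets the escalation patients apart from the analytic sample. In a descriptive trial, which patients are described is the main analysis decision for safety.

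**Conclusion.** The concern holds. The planned toxicity analysis is restricted to Cohort 5, and no by-cohort table, DLT listing or all-treated safety set appears anywhere in the document. On the stated accrual range this leaves out 37.5% to 75% of treated patients, and 37.5% to 55% across the range called most likely. These shares need only the protocol's own numbers. The chance of omitting at least one DLT (27% to 99%) rests on assumed rates of 5% to 30%, independence between patients, and one of two readings of the Cohort 3 entry text; the conclusion is the same under both. This is a gap in planned analysis and reporting, not in trial conduct. It should be fixed because it concerns a primary outcome and the data are already being collected.

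**What to change.** In Section 9.0:

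- Define the safety population as all patients given at least one dose of CPI-613.
- Tabulate the listed toxicities and all Grade 3 to 5 events by grade, for each dose cohort and overall, with Cohort 5 shown separately.
- List every DLT, giving for each cohort the number of patients who had a DLT or were followed through Cycle 1, the stated DLT period.
- Keep the efficacy analysis in the 10 Cohort 5 patients.

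Two contradictions must be reconciled before DLTs can be listed unambiguously. Section 6.1.1 requires probable or definite attribution to CPI-613 for a DLT, and Section 9.0 does not. The Cohort 2 and Cohort 3 paragraphs, which appear in both sections, disagree on when Cohort 3 opens. Which version applies is for the sponsor and investigator to settle.

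The analysis change costs a few sentences, one table and one listing, all from data already collected. The reconciliation also touches Section 6.1.1, so it goes beyond the statistical text, but it is needed in any case. The downsides are that escalation cohorts hold only 2 to 6 patients each, and that the overall column mixes doses and should be labelled as not being a rate at the selected regimen.

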5.1 Pre-Study Screening Tests and Safety Assessment

5.1.1 *Pre-Study Screening Tests*

Pre-study screening tests, which are also enrollment evaluations, must be performed according the following time frames:

Within 4 weeks: tumor assessments based on contrast CT of chest, abdomen, and pelvis, and optional blood and serum samples.

Within 2 weeks: medical history, physical exam, vital signs, height, weight, ECG, ECOG, evaluation of symptoms and medications, clinical chemistry, hematology, coagulation, and troponin I.

Within 1 week: pregnancy test for women of child-bearing potential.

5.1.2 *Safety Assessment*

The safety of CPI-613 will be assessed from the first dose to 1 month after last dose of CPI-613. The assessment will be based on:

- evaluation of symptoms
- vital signs
- ECOG performance status and survival
- clinical chemistry
- renal function
- hematology
- coagulation
- cardiac safety assessments via troponin I and ECG

The specifics of the safety tests are described in Section 5.2. All safety assessment tests are performed during screening (performed within 2 weeks prior to treatment with CPI-613 during Pre-Cycle 1), on Day 5 during Pre-Cycle 1, and prior to each treatment cycle with results available for review within 24 hrs before administration the anti-tumor agents. Chemistries, hematology, and renal function will also be performed on Days 1 and 4 of each treatment week during the first 2 cycles. ECOG performance status and survival will be assessed on Day 1 of each treatment week.

5.1.3 *Tumor Assessment*

Tumor response to treatment will assessed at baseline, and initially after the time frame encompassing the pre-cycle 1 treatment and the first three cycles using

Comprehensive Cancer Center of Wake Forest University
A Pilot Study: Open-Label Clinical Trial of CPI-613 in Patients with Advanced Bile Duct
Cancers
CCCWFU # 59212

contrast CT of the chest, abdomen and pelvis as well as serum levels of tumor marker CA-19-9 and performance status. Should the principal investigator determine that tumor progression has occurred the patient will be removed from the study. Should the principal investigator determine that the patient has stable disease or has had a favorable response, those patients will continue treatment with CPI-613 for an additional three cycles (approximately three months). At that time, patients will then undergo re-imaging contrast CT, CA-19-9 and performance status.

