For adverse events unrelated to serum creatinine elevation or reduction in renal function but are possibly related to CPI-613, the occurrence of Grade 1 toxicity does not generally require dose modification for subsequent doses for that patient. However, if Grade 2 toxicity (other than alopecia and nausea) probably related to CPI-613 develops, treatment is to be withheld and can resume only after the Grade 2 toxicity has been reduced to Grade 1 or below, and the dose level for subsequent doses for that patient will be reduced by 25% of the dose at which such Grade 2 toxicity occurs. Grade 2 alopecia and nausea do not require withholding treatment or dose reduction. If Grade 3 or 4 toxicity probably related to CPI-613 develops, dosing of CPI-613 of that patient will be withheld and the patient shall be monitored for recovery from, and reversibility of, such Grade 3 or 4 toxicity. To resume treatment with CPI-613 for a patient who has had CPI-613-related Grade 3 or 4 toxicity, the Grade 3 or 4 toxicity must be reduced to Grade 1 or below, and the dose level for subsequent doses for that patient will be reduced to 50% of the dose at which such Grade 3 or 4 toxicity occurs.

For adverse events related to creatinine elevation or reduction in renal function that are possibly related to CPI-613, dosing of the patient will be withheld even if the severity level is Grade 2 or above. Treatment can resume only after the toxicity has been reduced to Grade 1. The dose level for subsequent doses for that patient will be reduced by 15% if the severity level is of Grade 1, by 25% for Grade 2 toxicity, and by 50% for Grade 3 or 4 toxicity.

Furthermore, if the toxicity possibly related to CPI-613 is acute renal failure and the severity level is Grade 3 or 4, further patient enrollment will be temporarily suspended in order to enable assessment of the following aspects of the trial and implementation of corrective measures or protocol amendment, and if necessary:

- compliance of the study sites and investigators to the study protocol
- evaluation of the appropriateness of the procedures for monitoring renal function

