8.0 ADVERSE EVENTS LIST AND REPORTING REQUIREMENTS

8.1 Adverse Event Characteristics

- **CTCAE term (AE description) and grade:** The CTEP Active Version of the NCI Common Terminology Criteria for Adverse Events (CTCAE 4.0) will be utilized for AE reporting. The CTEP Active Version of the CTCAE is identified and located on the CTEP website at http://ctep.cancer.gov/protocolDevelopment/electronic_applications/ctc.htm. All appropriate treatment areas should have access to a copy of the CTEP Active Version of CTCAE.
- **‘Expectedness’:** AEs can be ‘Unexpected’ or ‘Expected’ (see Section 7.1 above) for expedited reporting purposes only.
- **Attribution of the AE:**
 - Definite – The AE *is clearly related* to the study treatment.
 - Probable – The AE *is likely related* to the study treatment.
 - Possible – The AE *may be related* to the study treatment.
 - Unlikely – The AE *is doubtfully related* to the study treatment.
 - Unrelated – The AE *is clearly NOT related* to the study treatment.

List of Adverse Events to be Reported:

Comprehensive Cancer Center of Wake Forest University
A Pilot Study: Open-Label Clinical Trial of CPI-613 in Patients with Advanced Bile Duct
Cancers
CCCWFU # 59212

*Abdominal pain
Alkaline phosphatase
ALT (SGPT)
Anorexia
AST (SGOT)
Bilirubin (hyperbilirubinemia)
Calcium (hypercalcemia, hypocalcemia)
*Creatinine
*Diarrhea
Flushing
Hemoglobin (anemia)
*Injection site Reaction
Leukocytes
Lymphopenia
*Nausea
Neutrophils (neutropenia)
Platelets (thrombocytopenia)
Potassium
Sodium
*Vomiting

All grade 3, 4, 5 adverse events should be reported on flowsheets and in ORIS regardless of whether they are on this list.

Asterisk (*) denotes expected Adverse Events.

All Serious Adverse Events (SAEs) which are Possibly, Probably or Definitely Related to CPI-613, and Unexpected are required to be reported to Cornerstone Pharmaceuticals via the provided SAE Reporting Form within 7 days. All completed forms must be sent to [name] at Cornerstone. Cornerstone will submit any applicable SAEs to the FDA.

SAE reports must be submitted to Cornerstone by fax or email to the following address:

Department of Regulatory and Clinical Affairs
Cornerstone Pharmaceuticals, Inc.
[name]
[name]
[contact]
Telefax: [contact] Email: [contact]

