9.0 STATISTICAL CONSIDERATIONS

This is a pilot study with the primary goal to be able to determine initial estimates of RR, and secondary goals to determine PFS and OS. Data from this trial will also provide additional data concerning the safety profile of the CPI-613 therapy. Since there is some uncertainty about what dose to examine for the 10 patients in this pilot study we propose the following pre-defined dose escalation scheme in order to determine the appropriate dose to provide to 10 patients with advanced bile duct cancers. This scheme has been discussed/proposed by the FDA and it is very specific and is described below. The dose-escalation scheme is based on the number of patients exhibiting dose-limiting toxicity (DLT), and DLT is defined as toxicity of Grade 3 or higher. The DLT determining period for all cohorts in the dose-escalation scheme is through the first cycle. Note – this section is redundant with section 6.1 but is included for completeness.

Cohort 1: The first 3 patients will not be treated with the 5 daily doses of CPI-613 during the pre-Cycle 1 week, and will only be treated with 3-weeks-on-1-week-off treatment cycles (see Table 6-1). The dose of CPI-613 will be 2,300 mg/m² (which is approximately three-quarters of the target dose). If none of these 3 patients develop a dose-limiting toxicity (DLT) through Cycle 1, the dose for the 3-weeks-on-1-week-off treatment cycles will be 3,000 mg/m² in all subsequent patients in this trial. However, if a DLT is observed in a patient (whether it is the 1st, 2nd or 3rd of the 3 intended patients), the number of patients in this cohort will be expanded to a maximum of 6 patients. If no DLT is observed in another patient out of a maximum of 6 patients, the dose for the 3-weeks-on-1-week-off treatment cycles will be 3,000 mg/m² in all subsequent patients in this trial. However, once DLT is observed in 2 patients, no additional patients will be treated at 2,300 mg/m² for the 3-weeks-on-1-week-off treatment cycles from that point on, even though the total number of patients in this cohort is as few as 2. The dose level of 2,300 mg/m², which induces a DLT in 2 or more patients, is considered to be above the maximum tolerated dose (MTD) for the 3-weeks-on-1-week-off treatment cycles. In this case, all subsequent patients in this trial will be treated at 1,700 mg/m² for the 3-weeks-on-1-week-off treatment cycles.

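### The planned safety table is tied to toxicities named in advance, so it may omit off-list events and the cardiac findings that the trial collects

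*Combined protocol and SAP*

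**What the plan says.** Section 2.2 makes safety a primary outcome alongside response rate. Under Proposed Analyses, Section 9.0 gives it one sentence: "We will also examine toxicities for these 10 patients by looking at each toxicity identified earlier in the protocol by grade".

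Section 8.1 contains the protocol's only enumerated set of toxicities, headed "List of Adverse Events to be Reported". It then adds: "All grade 3, 4, 5 adverse events should be reported on flowsheets and in ORIS regardless of whether they are on this list". There is no matching rule for Grade 1-2 events that are off the list.

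Three other places treat toxicity without reference to that list:

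- Section 5.1.2 includes "cardiac safety assessments via troponin I and ECG" among the safety assessments. Tables 5-1 and 5-2 schedule both tests at screening, on Days 1 and 5 of Pre-Cycle 1, and on Day 1 of each cycle.
- Section 6.2 acts on toxicity of almost any term: "if Grade 2 toxicity (other than alopecia and nausea) probably related to CPI-613 develops, treatment is to be withheld". The later dose for that patient is then reduced.
- For the escalation, Section 9.0 says that "DLT is defined as toxicity of Grade 3 or higher", with no restriction to listed terms.

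The Appendix C log has an open description field, Grades 1-5, attribution, and a column for the action taken on therapy.

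**The concern.** A safety table built from terms fixed before the data cannot show a toxicity that nobody foresaw, and Section 7.2 itself says that the drug's toxicity in humans is incompletely known. The protocol looks for cardiac effects at regular intervals, but its list gives them no row and Section 9.0 gives them no summary. It also changes dosing for Grade 2 events that Section 8.1 does not require anyone to report if they are off the list.

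What is at stake is how complete one of the two primary results is. A reader of the final table could take a missing row to mean that no event occurred, when the plan never undertook to count such events.

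**Working it through.** No stated figure in the plan bears on this point. The one precision figure, 0.31, is for the response rate. It reproduces as 1.96 × √(0.25/10) = 0.310 and has no counterpart for safety. The check is therefore mainly a comparison of sections.

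**Step 1: count the list in Section 8.1.** Gastrointestinal symptoms and anorexia, 5. Liver tests, 4. Creatinine, calcium, potassium and sodium, 4. Blood counts, 5. Flushing and injection-site reaction, 2. Total 5 + 4 + 4 + 5 + 2 = 20. No term covers troponin, ECG or any other cardiac finding. Glucose, albumin, magnesium and phosphate are tested under Section 5.2.2 and are also not listed.

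**Step 2: try each reading of the Section 9.0 sentence.** The sentence does not cite Section 8.1, so more than one reading is possible.

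| Reading of the toxicities meant | What the table covers | What it still leaves out |
|---|---|---|
| The 20-term list (most natural) | Listed terms, by grade | All off-list events; troponin I and ECG |
| List plus toxicities named in Section 6.2 | Adds alopecia and acute renal failure | All other off-list events; troponin I and ECG |
| List plus any Grade 3-5 event, from the Section 8.1 reporting rule | Adds off-list Grade 3-5 events | Off-list Grade 1-2 events; a summary of troponin I and ECG |

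The first two readings are sets fixed in advance and cannot show an unforeseen toxicity. The third can, but only from Grade 3 upward. No reading covers off-list Grade 2 events in general or provides a troponin and ECG summary.

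**Step 3: follow an off-list Grade 2 event judged probably related.** Section 6.2 withholds treatment and reduces later doses. Appendix C has space to record the event and the action taken. Section 8.1 does not require it to be reported, and Section 9.0 does not say that the log is what will be analysed. The event can change a patient's dosing and still be absent from the table.

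**Step 4: illustrate the size.** The documents give no rate for any off-list event, so the true rate p is an assumption. With independent patients, the chance of at least one case in 10 is 1 − (1 − p)^10:

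- p = 5%: 1 − 0.95^10 = 0.40
- p = 10%: 1 − 0.90^10 = 0.65
- p = 20%: 1 − 0.80^10 = 0.89
- p = 30%: 1 − 0.70^10 = 0.97

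These are probabilities that the event occurs, not that it goes unreported. They show that the affected events need not be rare.

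**Step 5: what a missing row is worth.** If a term is truly counted and 0 of 10 patients have it, the exact two-sided 95% upper limit is 1 − 0.025^(1/10) = 30.8%. If the term was never in the tabulation, its absence does not support even that weak bound.

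**The case against.** The strongest defence is that little is actually lost. Off-list Grade 3-5 events must go on flowsheets and into ORIS. Unexpected Grade 4 and all Grade 5 events go to the safety review committee. Serious, unexpected events at least possibly related to the drug go to the drug's supplier. Appendix C accepts any term and grade, and the dose rules in Section 6.2 presuppose that Grade 2 events are noted and graded. The sentence in Section 9.0 does not contain the word *only*. The trial is a descriptive pilot, and no sample size or decision rule changes.

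Much of this stands, and it limits the point. A reader might infer that off-list Grade 3-5 events disappear. The documents do not support that: such events are reported, and what is unclear is whether they are tabulated. A reader might also infer that the list could hide the very toxicity that set the dose. That does not follow either. Dose-limiting toxicities are counted without regard to the list, and those that set the dose arise in Cohorts 1-4. The toxicity sentence covers only the 10 patients of Cohort 5, so a dose-limiting event on a listed term would be missing from the table as well. That is a separate question about which patients are analysed. Nor should acute renal failure be presented as wholly uncovered: creatinine is listed, and the Grade 3-4 events that suspend enrolment are reportable in any case.

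What the defence does not answer is that reporting an event is different from analysing a primary outcome. A log that permits an entry does not require it, and nothing in Section 9.0 says that the log's contents will be tabulated.

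**Conclusion.** The point holds as a gap in the planned analysis and in the duty to report low-grade events. On the most natural reading, the table rests on 20 terms with no cardiac one. On the widest reading, off-list Grade 1-2 events and a troponin I and ECG summary are still missing. For a primary outcome this should be fixed, although it does not undermine the escalation or the response-rate estimate.

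The number of events that would be omitted cannot be computed from the documents. The range of 0.65 to 0.97 rests on an assumed true rate of 10% to 30% and on independent patients. The conclusion also rests on taking the Section 9.0 sentence as the whole of the planned safety analysis for these patients. No other safety analysis for them is stated.

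**What to change.** In Section 9.0, replace the toxicity sentence with text such as: *All recorded adverse events will be tabulated by CTCAE 4.0 term, maximum grade per patient and attribution. Events that led to dose delay, reduction or discontinuation will be listed. Troponin I and ECG findings will be summarised.*

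In Section 8.1, require adverse events of any term and any grade to be entered on the Appendix C log. Keep the 20-term list as a prompt and to mark which events are expected.

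The cost is wording in two sections and modest extra data entry for low-grade events on a form that already exists. No visit, test or sample-size change is needed.
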